## **11.4** Calculation or derivation of pharmacokinetic variables

The pharmacokinetic (PK) analyses will be performed at (or under the guidance of) AstraZeneca R&D. The actual sampling times will be used in the PK calculations. Details of the population kinetic analysis and the resulting outputs, which may include  $C_{max}$ ,  $t_{max}$ ,  $\lambda_z$ ,  $t_{2}$ , AUC $\tau$ , AUC CL/F, Vz/F and MRT will be documented in a Pharmacokinetic Analysis Plan prior to database lock

## **11.5** Calculation or derivation of pharmacodynamic variable(s)

The sputum sample: waking to 2-hour sample will be derived and analysed separately.

PD variables will be derived from blood and sputum samples separately.

Blood sample for PD markers will be collected at Visits 2 and 4. The corresponding measurements will be taken as the values of baseline and end of treatment. For each marker variable, the change from baseline will be used as the endpoint.

The sputum samples will be collected at timings specified in Table 3. The inflammatory markers will be derived from the sputum samples. For each of inflammatory markers, the geometric mean of the values prior to treatment (Visit 1a, Visit 1b and Visit 2) will be used as baseline, and the change from baseline to end of treatment (geometric mean of the values at Visit 3a, Visit 3b and Visit 4) will be used as the endpoint.

# **11.5.1** Calculation or derivation of the relationship between pharmacokinetic and pharmacodynamic variables

The relationship between plasma AZD5069 concentrations, exposure and/or dose with AEs, pharmacodynamic (PD) parameters and/or clinical endpoints will be investigated using a PK/PD approach. The PK/PD analyses will be performed at (or under the guidance of) AstraZeneca R&D. The actual sampling times will be used in the PK calculations. Details of the population kinetic analysis and the resulting outputs will be documented in a Pharmacokinetic Analysis Plan prior to database lock.

## **11.6** Calculation or derivation of pharmacogenetic variables

Details can be found in Appendix D.

# 11.7 Calculation or derivation of health economic variables (not applicable)

Approve

68(76)

PRINTED COPY OF

¢

ы И

THIS

AN ELECTRONIC DOCUMENT. PLEASE CHECK ITS VALIDITY BEFORE USE

#### 12. STATISTICAL METHODS AND SAMPLE SIZE **DETERMINATION BY ASTRAZENECA OR** REPRESENTATIVE

A comprehensive statistical analysis plan (SAP) will be prepared before database lock and unblinding of the data in order to avoid any potential bias due to knowledge of the treatment received.

using SAS® version 8.2 and, Statistical analyses will be performed by Quintiles UK, where appropriate, additional validated software. These analyses will be performed in accordance with the SAP, which will detail analyses to be performed, define analysis sets, and summaries to be produced for the CSR.

Pharmacokinetic and pharmacodynamic analyses will be carried out by AstraZeneca.

#### **Description of analysis sets** 12.1

#### 12.1.1 All subjects analysis set

This analysis set comprises all patients screened for the study and will be used for reporting of disposition and screening failures.

#### 12.1.2 Efficacy analysis set

All patients who have received at least one dose of Investigational Product and have post-dose data available will be included in the efficacy analysis set. Unless there is evidence to the contrary, it will be assumed that errors where patients receive treatment other than the one they were randomised to, were genuine and patients will be summarised according to the treatment they actually received. It is probable that this dataset will be the same as the safety analysis set. All efficacy (excluding PK and PD) analyses and summaries will be based on this analysis set.

#### 12.1.3 Safety analysis set

All patients who have received at least one dose of IP and have post-dose data available will be included in the safety analysis set. Patients will be summarised according to the treatment they actually received irrespective of what treatment they were randomised to. All safety summaries will be based on this analysis set.

#### 12.1.4 PK analysis set

All patients receiving AZD5069 and for whom PK blood samples assumed not to be affected by factors such as protocol violations (eg, disallowed medication) are available from, will be included in the PK analysis set. All PK summaries will be based on this analysis set.

GEL Version ID: RITA.000-335-908.4.0

Approved by

69(76)

#### 12.1.5 PD analysis set

All patients receiving at least 1 dose of IP and for whom PD samples are available (assumed not to be affected by factors such as protocol violations) will be included in the PD analysis set. All PD summaries will be based on this analysis set.

#### 12.1.6 Per protocol analysis set

The blinded data will be investigated during the blind review of the data and if appropriate, a per protocol analysis set may be defined. This will be a subset of the efficacy analysis set, excluding patients who have had a major protocol deviation which could influence the data. Analyses to be performed using this dataset will be defined in the SAP.

## 12.2 Methods of statistical analyses

A SAP will be produced including details of the assumptions being made about the data, the analyses to be performed on the data and the analysis sets upon which these will be based, and how issues such as missing data and multiplicity will be dealt with.

Demography and baseline characteristics will be summarised for each treatment group based on the treatment they actually received and overall, but will not be statistically tested since the study is randomised and it is therefore assumed that any differences between the treatment groups would be random.

#### 12.2.1 Primary outcome variable

The primary outcome variable is:

• Change from baseline (geometric mean of the values at Visit 1a, 1b and 2) to treatment (geometric mean of the values at Visit 3a, 3b and 4) in sputum absolute neutrophils.

The primary outcome variable will be compared between AZD5069 and placebo using an analysis of variance (ANOVA) model with fixed factors treatment and country (or centre) and using baseline as a covariate. Two-sided 90% confidence intervals (CIs) will be constructed for the treatment difference and p values given. If the assumptions of ANOVA are violated, data transformation (eg, log-transformed) may be utilized or an appropriate non-parametric technique (eg, Wilcoxon rank sum) will be used instead.

The primary outcome variable analysis will be carried out on the PD analysis set.

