## 5.2.1 Procedures for randomisation

A dynamic randomisation approach will be applied. Randomisation codes will be generated by the Interactive Voice Response System (IVRS) / Interactive Web Response System (IWRS) provider using minimisation with biased coin assignment method which assigns patients to treatments in a clinical trial with stratifying factors on which it is desired to achieve balance.

Patients will be assigned to treatment groups using IVRS/IWRS. Routines for this will be described in the IVRS/IWRS user manual that will be provided to each centre. Randomisation codes will be assigned to patients who are eligible for randomisation.

Randomisation will be stratified for 1) use of inhaled corticosteroids and 2) pseudomonas aeruginosa infection (past or current). Patients will be randomly allocated to AZD5069 80 mg bd or placebo in a 1:1 ratio. Patients who are withdrawn after randomisation will not be replaced.

The randomisation code will be loaded into AstraZeneca Global Randomisation System (GRand).

PLEASE CHECK ITS VALIDITY BEFORE USE

AN ELECTRONIC DOCUMENT.

A PRINTED COPY OF

5 H

THIS

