## 11. EVALUATION AND CALCULATION OF VARIABLES BY ASTRAZENECA OR DELEGATE

## **11.1** Calculation or derivation of efficacy variable(s)

#### 11.1.1 Differential cell count (absolute and percentage neutrophils) in sputum

The geometric mean of the values from Visit 1a, 1b and 2 will be used as baseline for differential cell count. The change from baseline to treatment (geometric mean of the values at Visits 3a, 3b and 4) will be used as outcome variable(s). The other differential counts will be reported for completeness.

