## **12.3** Determination of sample size

The sample size for this study was selected in accordance with the research hypothesis as described in Section 1.2.

Data from a previous study in bronchiectasis patients showed that the standard deviation of the differences in absolute sputum neutrophils between the active and placebo groups was approximately 1. Assuming that the standard deviation (SD) would be similar in this study, 25 patients in each treatment group would be required to detect a 50% decrease in neutrophils, using a 1-sided test with a 5% significance level (SL) and 80% power. In order to ensure that we have data on this number as a minimum, it is intended to randomise 30 patients into each treatment group; ie, a total of 60 patients.

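### The primary analysis defaults to untransformed change in sputum neutrophils, but the sample size rests on a relative effect and a unitless SD, so the stated 80% power is not shown for the raw-change ANOVA or its Wilcoxon fallback

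*Protocol*

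**What the plan says.** **Primary variable and model.** Section 12.2.1 words the primary variable as "Change from baseline (geometric mean of the values at Visit 1a, 1b and 2) to treatment (geometric mean". The on-treatment mean is taken over Visits 3a, 3b and 4, and the variable is the absolute neutrophil count. Section 11.1.1 also defines a change, not a ratio or a difference of logs. The model is ANOVA with treatment and country (or centre) as fixed factors and baseline as covariate, with a two-sided 90% CI for the treatment difference. No transformation is part of this default.

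**Fallback.** The same section adds: "If the assumptions of ANOVA are violated, data transformation (eg, log-transformed) may be utilized or an appropriate non-parametric technique (eg, Wilcoxon rank sum". The synopsis says the same. Neither place gives a criterion for violation or an order between transformation and rank test.

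**Sample size.** Section 12.3 reports from a previous bronchiectasis study that "the standard deviation of the differences in absolute sputum neutrophils between the active and placebo groups was approximately 1". It concludes that "25 patients in each treatment group would be required to detect a 50% decrease in neutrophils". The calculation is one-sided at 5% with 80% power. To protect that number, "it is intended to randomise 30 patients into each treatment group". Neither the scale of the SD nor an expected mean count is given.

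**The concern.** A percentage decrease is a ratio, and averaging the three samples in each period by geometric mean treats the counts as multiplicative. Both fit a log-scale analysis. The default test compares untransformed changes instead. A raw difference does not estimate a percentage reduction, and patients with the highest counts dominate it. The Wilcoxon alternative, run as a plain rank-sum test, drops the baseline and country terms and gives no percentage estimate.

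Section 12.2.2 treats all testing apart from the primary variable as exploratory, so this is the trial's one formal comparison. At stake are whether its power is the power stated, and whether the result answers the question the trial was sized for.

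**Working it through.** **Inputs from the protocol.** One-sided α = 0.05 (z = 1.645), power 0.80 (z = 0.842), SD = 1, 50% decrease, 25 per group, 30 per group randomised (section 12.3); 1:1 allocation (section 5.2.1).

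**Step 1: reproduce 25 per group.** For two parallel groups, n per group = 2(1.645 + 0.842)² SD²/δ². With SD = 1 the numerator is 12.37.

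| Reading of SD 1 and 50% | δ | n per group |
|---|---|---|
| natural log | ln 2 = 0.693 | 25.7 |
| log base 10 | 0.301 | 136.5 |
| log base 2 | 1 | 12.4 |
| raw difference of 0.5 | 0.5 | 49.5 |

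Only the natural-log reading comes close to 25. Power there is Φ(0.693/√(2/25) − 1.645) = Φ(2.451 − 1.645) = Φ(0.806) = 79%. With the t distribution it is 78.0% at 25 and 84.3% at 30 per group.

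**Step 2: read the SD as raw units.** A 50% decrease then equals half the mean count, which is not given. The required n per group would be 198 for a mean of 0.5, 50 for 1, 26 for 1.39 and 13 for 2. Power for the untransformed analysis cannot be derived from the document.

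**Step 3: compare the candidate analyses.** This needs assumptions that the protocol does not supply: lognormal counts, 25 per arm, true ratio 0.5, SD of the log change fixed at 1, equal log variance in both periods, no country term, one-sided 5%. Baseline log SD s varies from 0.75 to 1.5. Fixing the SD of change at 1 implies a baseline-to-treatment correlation of 1 − 1/(2s²).

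| Baseline log SD | Implied correlation | Log ANCOVA | Raw-change ANCOVA | Wilcoxon on raw change |
|---|---|---|---|---|
| 0.75 | 0.11 | 94% | 89% | 60% |
| 1.0 | 0.50 | 87% | 70% | 60% |
| 1.25 | 0.68 | 83% | 57% | 58% |
| 1.5 | 0.78 | 81% | 45% | 55% |

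Reruns agree within about two percentage points. Log ANCOVA exceeds the 78% of step 1 because adjusting for baseline reduces the residual SD. At s = 1, for example, it is √(1 − 0.5²) = 0.87.

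**Step 4: vary the structure.** With a residual log SD of 1 and correlation 0 to 0.7, log ANCOVA has about 77% power and raw-change ANCOVA 63 to 45%. With the log change independent of baseline and baseline log SD 0.5 to 1.5, log ANCOVA has 77 to 78% and raw-change ANCOVA 58 to 35%. Log ANCOVA is ahead throughout.

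**Consistency of α.** A two-sided 90% CI matches a one-sided 5% test, so that part needs no change.

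**The case against.** **The raw analysis would rarely survive.** In the step 3 scenarios a Shapiro-Wilk test at 5% (an assumed choice of check) rejects normality of the raw residuals in about 96 to 100% of trials. If log transformation follows, power is 81 to 94%. This stands, and it moves the practical weakness from the raw default to the unranked choice that follows it: if the choice falls on Wilcoxon applied to the raw change, power is 55 to 60%.

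**The log scale is not stated.** This also stands. A one-sample formula with δ = 0.5 gives (1.645 + 0.842)²/0.25 = 24.7, which rounds up to exactly 25, while ln 2 gives 26 after rounding up. The one-sample formula is wrong for two parallel groups and would leave about 55% power at 25 per group, so it does not rescue the plan. It could still be where 25 came from. A reader might infer that the SD of 1 is certainly a natural-log SD; the protocol does not support that certainty.

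**The power loss is not a property of the document.** A reader might also infer that the trial is underpowered as written. At baseline log SD 0.75 the raw analysis still has 89% power, and the spread and correlation that decide this are not in the protocol.

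**The SAP may settle it.** Section 12.2 leaves details of assumptions to an SAP, which section 12 requires before database lock and unblinding. That protects against choosing a method with the treatment codes known. It does not remove the point: the protocol already fixes a default scale and two unranked alternatives, and these do not match its own sizing basis.

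**Conclusion.** The point holds as a mismatch between the stated primary analysis and the stated basis for the sample size. Among standard two-group readings, 25 per group corresponds only to a natural-log comparison. On a raw-unit reading no power can be computed. Either way, 80% power is not shown for the raw-change ANOVA or for the Wilcoxon fallback.

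The loss is conditional. It runs from a few percentage points (94 against 89%) to more than thirty (81 against 45%) across the step 3 assumptions. Only the direction is stable: log-scale ANCOVA had the highest power in every scenario examined.

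This should be fixed. It does not invalidate the design, because log transformation is already a named option and, if the SD is a natural-log SD, the planned numbers nearly deliver the stated power.

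**What to change.** - **Sections 12.2.1 and 11.1.1, and the synopsis:** for the absolute count, define the primary variable as ln(geometric mean of Visits 3a, 3b and 4) minus ln(geometric mean of Visits 1a, 1b and 2). Analyse it by ANCOVA with treatment, country (or centre) and ln(baseline). Back-transform to an AZD5069/placebo ratio with its 90% CI. Keep a rank method as a sensitivity analysis only.
- **Section 12.3:** have the sponsor state the scale of the SD from the source study. If it is natural log, restate the unadjusted power as about 78 to 79% at 25 per group and about 84% at 30. If it is another scale, redo the calculation.

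The cost is wording in these sections and matching text in the SAP, settled before unblinding. On the natural-log reading no extra patients or data are needed.

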## 12.2.2 Secondary outcome variables

The secondary outcome variables are:

• Change from baseline (geometric mean of the values at Visits 1a, 1b and 2) to treatment (geometric mean of the values at Visit 3a, 3b and 4) in percentage neutrophils.

Approved

Date

ELECTRONIC DOCUMENT.

AN

ĿЮ

PRINTED COPY

К

5 H

THIS

PLEASE CHECK ITS VALIDITY BEFORE USE

- Change from baseline (Visit 1a or Visit 1b) to end of treatment (Visit 4) in 24-hour sputum collection weight.
- Change from baseline (Visit 2) to treatment (Visit 4) in FEV1.
- Change from baseline (Visit 2) to treatment (Visit 4) in SVC.
- Change from baseline (Visit 2) to treatment (Visit 4) in FEF25-75.
- Change from baseline (Visit 2) to treatment (Visit 4) in FVC.
- Change from baseline period (mean of last 7 days prior to start of treatment) to treatment period (mean of the last 7 days on treatment) in symptom score diary card (Bronkotest©).
- Change from baseline (Visit 2) to treatment (Visit 4) in mean total score and domain scores from St George's Respiratory Questionnaire.
- Change from baseline to treatment in sputum inflammatory markers including, but not limited to (and subject to the availability of validated assays): TNF-α, IL-8, IL-6, IL-1β, RANTES, MCP-1, GRO-α.
- Change from baseline to treatment in blood inflammatory markers including, but not limited to (and subject to the availability of validated assays): neutrophil concentration, TNF-α, IL-8, high sensitivity CRP, Amyloid-A, IL-6, IL-1β, GRO-α.
- Pharmacokinetic parameters (AZD5069 concentration measured in plasma).

The secondary outcome variables from the Bronkotest© diary card (continuous variables only), St George's Respiratory Questionnaire, lung function, 24-hour sputum weight, sputum and blood collections will be compared between AZD5069 and placebo using an analysis of variance model with fixed factors treatment and country (or centre) and using baseline as a covariate. Two-sided 90% CIs will be constructed for the treatment difference and p values given. For variables with a skewed distribution, data may be log-transformed prior to analysis or a non-parametric test (Wilcoxon rank sum) used instead. In addition, the statistical analysis and summary will be produced for data derived from BDI/TDI. The further details will be provided in the SAP.

Whilst statistical testing is being performed, with the exception of the primary variable, such testing is deemed to be exploratory and as such no multiplicity corrections will be made.

No formal statistical analysis will be carried out on the other secondary outcome variables.

AEs will be summarised by means of descriptive statistics and qualitative summaries. AEs will be listed for each patient and summarised by System Organ class and Preferred Term assigned to the event by using MedDRA. Laboratory safety variables will be summarised

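### The Wilcoxon fallback for skewed variables drops the baseline covariate and country factor of the planned model; a rank ANCOVA on the change would keep both

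*Protocol*

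**What the plan says.** Sections 12.2.1 and 12.2.2 and the synopsis (Statistical methods) plan an analysis of variance with treatment and country (or centre) as fixed factors and baseline as a covariate, reported with a two-sided 90% confidence interval. The outcomes at issue are changes from baseline. For the sputum cell counts, Section 11.1.1 states: "The geometric mean of the values from Visit 1a, 1b and 2 will be used as baseline for differential cell count".

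Two fallbacks follow.

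- **Secondary variables (12.2.2):** "For variables with a skewed distribution, data may be log-transformed prior to analysis or a non-parametric test (Wilcoxon rank sum) used instead". The rank-sum test is named outright.
- **Primary variable (12.2.1, repeated in the synopsis):** if the assumptions fail, a transformation may be used or "an appropriate non-parametric technique (eg, Wilcoxon rank sum) will be used instead". Here the rank-sum test is only an example.

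Neither section ranks the log transformation, which keeps the planned model, above the rank test. Neither mentions a rank method that keeps the covariates. Section 12.2.2 calls all testing other than that of the primary variable exploratory.

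**The concern.** A two-sample rank-sum test has no place for a covariate or a factor. Once the plan moves to it, the adjustment for baseline and country goes. Baseline is then used only by subtraction, with its slope fixed at 1. The best slope is the correlation times the ratio of on-treatment SD to baseline SD. When that is below 1, subtraction removes too much, which adds variance and leaves the comparison open to chance imbalance at baseline. The minimisation in Section 5.2.1 balances inhaled corticosteroid use and pseudomonas infection, not baseline sputum values.

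The branch may well be used. The variables concerned include sputum neutrophil counts, 24-hour sputum weight, and cytokines in sputum and blood. The protocol already treats the sputum counts and markers as multiplicative by averaging them geometrically. At stake is precision that data already being collected could supply.

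**Working it through.** **Inputs from the protocol (Sections 12.3 and 5.2.1).** The test: "using a 1-sided test with a 5% significance level (SL) and 80% power". The SD: "the standard deviation of the differences in absolute sputum neutrophils between the active and placebo groups was approximately 1". The effect: 25 per group "would be required to detect a 50% decrease in neutrophils". Size: "it is intended to randomise 30 patients into each treatment group; ie, a total of 60 patients". Allocation is 1:1.

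**Assumptions.** The SD has no stated scale; I read it as the SD of the natural-log change. The baseline to on-treatment correlation ρ is not given; I use 0.3 to 0.8, with equal variances at the two times.

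**The plan's own figure.** With δ = ln 2 = 0.693:

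n = 2 × ((1.645 + 0.842) / 0.693)² = 25.7, so 26 per arm against the stated 25.

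Power at 25 = Φ(0.693 / √(2/25) − 1.645) = Φ(0.806) = 79.0%.

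Other readings do not fit: δ = 0.5 gives 50 per arm, log2 gives 13, log10 gives 137. The calculation is unadjusted, so the sample size does not rely on the covariate.

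**Formula comparison if the log scale is normal.** With SD of change 1, the ANCOVA residual SD is √((1 + ρ)/2). Wilcoxon has relative efficiency 0.955.

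- Wilcoxon, 25 per arm: Φ(2.451 × √0.955 − 1.645) = 77.3% at every ρ.
- Log-scale ANCOVA, ρ = 0.5: Φ(2.451 / 0.866 − 1.645) = 88.2%. At ρ = 0.3, 0.7 and 0.8: 91.8%, 84.5% and 82.6%.
- Difference: 14.5, 10.9, 7.1 and 5.3 points at ρ = 0.3, 0.5, 0.7 and 0.8. At 30 per arm it is 11.8 down to 4.6.

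**Simulation of the fallback itself.** 25 per arm, three country levels, shift ln 0.5, 1-sided 5%, 4,000 trials per cell (standard error under 1 point). Log values are normal, t with 3 degrees of freedom, or normal with 10% of values at five times the SD, all scaled to an SD of log change of 1. Rank ANCOVA regresses the ranked change on treatment, ranked baseline and country. Power in %:

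| Log data | ρ | Log ANCOVA | Wilcoxon, log change | Rank ANCOVA, log change | Wilcoxon, raw change | Rank ANCOVA, raw change |
|---|---|---|---|---|---|---|
| Normal | 0.3 | 90.4 | 75.0 | 87.1 | 58.8 | 80.9 |
| Normal | 0.5 | 85.8 | 75.6 | 83.9 | 58.0 | 73.6 |
| Normal | 0.7 | 82.9 | 76.4 | 80.9 | 56.1 | 68.7 |
| Normal | 0.8 | 80.7 | 75.6 | 78.3 | 55.0 | 64.7 |
| t(3) | 0.3 | 91.3 | 90.3 | 96.6 | 78.8 | 95.0 |
| t(3) | 0.8 | 84.0 | 92.2 | 94.2 | 75.8 | 87.3 |
| Contaminated | 0.3 | 89.0 | 94.6 | 98.5 | 86.8 | 97.3 |
| Contaminated | 0.8 | 81.5 | 96.0 | 97.0 | 84.1 | 93.6 |

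Rank ANCOVA beats Wilcoxon in every cell. On log change the gain is 12 down to 3 points with normal log data and 6 down to 1 with heavy tails. On the raw change the table gives about 10 to 22 points. A second, independent set of runs gave 13 to 3, 1 to 6 and 6 to 21 points. The upper ends agree within simulation error; I quote the second set's lower end of 6 as the more cautious figure.

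**The case against.** A reader might infer that the fallback costs 5 to 15 points of power. The calculation does not support that. The figure is the loss against log-scale ANCOVA when log values are normal, and there the log transformation makes the planned model valid, so no rank test is needed. With heavy-tailed log data, where a rank test would be wanted, plain Wilcoxon mostly matches or beats log-scale ANCOVA (92.2% against 84.0% with t(3) data at ρ = 0.8). This objection stands: the 5 to 15 points argue for putting the log transformation first and do not price the fallback.

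Other stronger readings also fail.

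- *Baseline is thrown away.* It is still subtracted; only the covariate adjustment is lost. It is also not always a triplicate: Sections 11.1.2 and 11.5 use a single value for 24-hour sputum weight and for blood markers.
- *No interval is available.* The rank-sum test has a Hodges-Lehmann estimate with a 90% confidence interval; it is simply not covariate-adjusted.
- *Subtraction always over-corrects when ρ is below 1.* Not if the on-treatment SD is enough larger than the baseline SD.
- *The trial becomes underpowered.* The sample size was unadjusted. By formula Wilcoxon has 77.3% at 25 per arm against 79.0% for that calculation, and 83.6% at the intended 30.

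Finally, the wording is permissive, and a SAP could settle the procedure. That holds for the primary variable, where the rank-sum test is only an example and a rank ANCOVA already fits the text. It holds less for Section 12.2.2, which names the test and would have to be departed from.

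**Conclusion.** The point holds in a modest form. The protocol names a fallback that cannot carry the baseline and country terms of its own model, although a rank method that carries both did better in every setting tried. Under the planning inputs the gain over plain Wilcoxon is about 13 down to 3 points on log-normal change as ρ rises from 0.3 to 0.8, about 1 to 6 points with heavy-tailed log data, and about 6 to 21 points on the untransformed change.

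These figures rest on an assumed ρ, on SD 1 being on the natural-log scale, and on the primary variable's inputs. The protocol states no power for the secondary variables. Because those tests are exploratory, the consequence falls mainly on the primary variable.

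**What to change.** In the synopsis, 12.2.1 and 12.2.2, set an order for skewed variables:

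1. Log-scale ANCOVA with baseline and country (or centre), reported with its 90% confidence interval.
2. If its assumptions still fail, rank ANCOVA: ranked change on ranked baseline, with treatment and country (or centre).
3. Plain Wilcoxon as a supportive check, with its Hodges-Lehmann estimate and 90% confidence interval.

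Two alternatives should not be preferred at step 2. A permutation test of the log-scale ANCOVA coefficient uses the same statistic as that ANCOVA, and so can lose to Wilcoxon with heavy tails. Ranking the on-treatment value instead of the change lost up to about 5 points to Wilcoxon at ρ = 0.8 with heavy-tailed data.

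The cost is a wording change and a few lines of code, with no new data or patients. The downside is a method slightly less familiar to readers.
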